#### **10.10. Tanner Staging**

Tanner Staging will be assessed for subjects >7 years old during the study at baseline period (Visit 3) and End of study (Visit 12). Conceptually, pubertal maturation can be described in terms of sequence, timing, and tempo. Puberty consists of a series of predictable events, and the sequence of changes in secondary sexual characteristics has been categorized by several groups. The onset and progress of pubertal changes will be recorded on a 5 point scale for boys and girls separately. Boys are rated for genital development and pubic hair growth through stage I to stage V. Girls are rated for breast development and pubic hair growth through stage I to stage V.

The number and percentage of subjects in each Tanner Stage will be presented for all visits by treatment group separately for boys and girls overall and also broken out for the following age groups:

- >7 years to <=11,
- >11 years to <=15,

**This document is confidential.**

>15 years to <=18.

All Tanner staging data will be presented in the subject data listing.

### 10.11. Columbia-Suicide Severity Rating Scale

Columbia-Suicide Severity Rating Scale data will be collected as per at screening visit (Visit 1), at randomization (visit 3), Titration period (at visit 6), maintenance period (at Visit 8 and 10) and at End of study visit (Visit 12).

Subjects who are younger than 7 years chronologically, or who are judged by the investigator not to have the mental capacity to understand the questions as specified on the C-SSRS, will not complete the rating. The investigator should use his/her judgment to substitute intellectually-appropriate questions to probe the tendency for self-harm.

If a subject with the intellectual capacity to complete the C-SSRS has their 7th birthday during the study, use of the C-SSRS should be initiated at subsequent visits.

All individual subject C-SSRS data will be listed.

#### Suicidal Ideation:

The following outcomes are C-SSRS categories for suicidal ideation and have binary responses (yes/no):

Category	Outcome Description

Suicidal ideation is assessed as a "yes" answer at any time during the T + M period to any one of the five questions (1-5) above. The number and percentage of subjects with suicidal ideation will be presented, as well as the number and percentage having a "yes" response to each category (1-5) at least once during the T + M period. The denominator will be the number of subjects completing the C-SSRS at least once during the T + M Treatment period.

#### Suicidal Behavior:

The following outcomes are C-SSRS categories for suicidal behavior and have binary responses (yes/no):

Category	Outcome Description

This document is confidential.

**Statistical Analysis Plan**

Sponsor: Zogenix International Limited; Protocol No.: ZX008 Study 2 (ZX008-1501 and ZX008-1502)

Suicidal behavior is assessed as a “yes” answer at any time during the T + M period to any one of the five questions (6-10) above. The number and percentage of subjects who had suicidal behavior, as well as the number and percentage having a “yes” response to each category (6-10) at least once during the T + M period. The denominator will be the number of subjects completing the C-SSRS at least once during the T + M period.

**Suicidal Ideation or Behavior:**

An overall composite will be provided similar to the suicidal ideation and behavior endpoints, but will instead count a subject if any of the C-SSRS questions 1 through 10 are marked as ‘yes’ anytime during the T+M period.

**Self-injurious behavior without suicidal intent:**

The number and percentage of subjects having reported anytime during the T+M period experiencing a ‘Self-injurious behavior without suicidal intent’ event (Question 11) will be provided.

**10.12. Brief Rating Inventory of Executive Function (BRIEF and BRIEF-P)**

The Behavior Rating Inventory of Executive Function (BRIEF™) and its preschool version, BRIEF-P, are standardized, validated rating scales to measure executive function in children within the home and school environments that will be assessed by the parent according to the schedule in Table 1 (i.e. at Randomization (Visit 3), at Maintenance period (Visit 8) and at End of study visit (Visit 12)).

The BRIEF measures multiple aspects of executive functioning; scales include Inhibit, Shift, Emotional Control, Initiate, Working Memory, Plan/Organize, Organization of Materials and Monitor.

The original BRIEF was the basis for the development of the BRIEF-P. The BRIEF-P Rating Form consists of 63 items that measure various aspects of executive functioning: Inhibit, Shift, Emotional Control, Working Memory, and Plan/Organize.

For the BRIEF and the BRIEF-P, mean scores at Baseline, End of Study/ET and mean change from baseline to End of Study/ET, and descriptive statistics will be presented by treatment group for the Safety population (SAF).

This document is confidential.

## 11. Interim Analyses

No formal interim analysis is planned for Study 2.

Unblinding for Study 2 will not occur until data cleaning is completed and all decisions regarding protocol deviations warranting exclusion from the per protocol population have been made.

This document cannot be used to support any marketing authorization application and any extensions or variations thereof.

PUBLIC COPY

This document is confidential.

## 12. Changes from Analysis Planned in Protocol

- The 1501 and 1502 protocols set a target that 40% of enrolled subjects to be less than 6 years old, but candidate subjects have been older than expected. Consequently, the enrollment target has been revised to ensure that at least 25% of subjects are less than 6 years old.
- Protocols 1501 and 1502 state that efficacy and safety endpoints will be repeated separately for the titration and maintenance periods, however this is not planned to be conducted –Data from the T+M Period will be summarized and analyzed for all endpoints, and separate analyses of titration or maintenance periods will be generated only for selected endpoints.
- Protocols 1501 and 1502 state that analyses of safety data will be presented by treatment actually received. However, safety data will be presented by randomized treatment group except where noted otherwise.
- Protocols 1501 and 1502 provide sample size calculations to support a total study sample of 105 subjects, 35 per treatment group. A revised sample size calculation has increased the sample size to 40 subjects per treatment group, for a total of approximately 120 subjects.
- Protocols 1501 and 1502 state that a sensitivity analysis for the primary efficacy endpoint will be conducted by adding a factor indicating whether a subject had a change in prescribed dose or type of concomitant AED medication during the T+M Period, however this is not planned to be conducted. Instead it is planned to compare the treatment groups with respect to the proportion of subjects who changed dose and/or type of AED concomitant medication during the T+M Period.
- Protocols 1501 and 1502 state that the longest interval between convulsive seizures will be analyzed using a log-rank test. However, further considerations of this endpoint suggest that while the first seizure-free interval may be subject to independent censoring, the second and later seizure-free intervals are subject to dependent censoring. Moreover, the last seizure-free interval is subject to intercept sampling, hence a longer seizure-free interval is more likely to be censored. Finally, the number of seizures or seizure-free intervals is informative about the underlying distribution, as subjects at a higher risk of experiencing recurrent events are likely to have shorter and hence more seizure-free intervals during the 84 day treatment period. Thus, a simple analysis comparing medians of the largest seizure free intervals was proposed.
- Responder analyses – Protocols 1501 and 1502 include a  $\geq 40\%$  response analysis as one of the key secondary endpoints. It was decided to not include this endpoint as the  $\geq 50\%$  response analysis is considered clinically meaningful.
- An analysis of the percentage of subjects who achieve a 25% reduction in seizures was added. The number of subjects whose seizures worsen during the study will be included, along with the percentage of worsening.
- The Protocol states that the BRIEF rating scale will be used to evaluate cognition in children aged 2-18. The BRIEF-P will be used for children aged 2-4, and the BRIEF will evaluate children aged 5-18.
- The protocol included the exploratory objective to compare the ZX008 0.2 mg/kg/day and ZX008 0.8 mg/kg/day doses on primary, secondary, safety, and PK endpoints. Comparisons between doses were not made using inferential statistics.
- The protocol states that subjects will enter information daily into the diary; in some cases, data could not be entered directly into the diary and had to be entered via the DCR process. These data were analyzed in the same manner as data entered directly.
- An analysis of the percentage of subjects who achieve a 100% reduction (near seizure-free) in seizures was added. The number of subjects whose seizures worsen during the study will be included, along with the percentage of worsening.
- Intermediate missing day and post-discontinuation imputation was added: Intermediate missing days should be imputed as the worse observed outcome for that patient if the patient was assigned to an active arm or zero seizures if the patient was assigned to placebo. For patients who discontinued the study, the day of discontinuation should be imputed as the worse observed outcome if assigned to ZX008 and as zero counts if the patient was assigned to placebo. The remaining days should be imputed using the baseline seizure counts for all arms.

This document is confidential.

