## Statistical Analysis Plan

Sponsor: Zogenix International Limited; Protocol No.: ZX008 Study 2 (ZX008-1501 and ZX008-1502)

a target of  $\geq 25\%$  of subjects in each age group. Subjects were assigned a randomization number by IWR system upon confirmation that the subject qualified for enrollment in the Titration Period. Once a randomization number was assigned to a subject, the site recorded the subject's initials and identification number on the corresponding study drug bottles.

Each bottle contained the assigned treatment (ZX008 0.2 mg/kg/day, ZX008 0.8 mg/kg/day, or placebo). ZX008 and placebo were identical, thus rendering the study drug and placebo indistinguishable. The blinding scheme instituted for this study ensured that the volume of study medication taken could not be associated with the dose group, thus unblinding the study. This was achieved by random assignment of different concentrations of the ZX008 oral solution (1.25 mg/mL, 2.5 mg/mL, and/or 5 mg/mL) by the IVR/IWR system. The IWR system instructed site personnel to the volume of oral solution to be administered based on that subject's weight. (Dose was to be recalculated by the system once at the midpoint of the study.) During the Titration, Maintenance, and Taper/Transition Periods, the subjects and study personnel (investigators, clinical staff, personnel involved in data collection and analysis, the Medical Monitor, and the sponsor) were blinded to the treatment allocation and to the concentration of ZX008 oral solution.

Prior to database lock for Study 1 an unblinding plan was implemented. The purpose of unblinding plan was to provide specific information and guidance to the Clinical Development Team, Clinical Operations Team, Biostatistics, Project Management, and other functions regarding plans for unblinding key team members for analysis of Study 1 top-line data and final Tables, Listings, and Figures (TLFs). 'Unblinding' is defined as having access to subject-level data (i.e., subject data listings or the randomization codes) that provides information regarding randomized dose group, treatment effect, and safety. Access to aggregated data (ie, group-level tables and figures) does not constitute 'unblinding' and for the purposes of data cleaning and database lock, these individuals were still considered 'blinded'.

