**Statistical Analysis Plan**

Sponsor: Zogenix International Limited; Protocol No.: ZX008 Study 2 (ZX008-1501 and ZX008-1502)

maximum of 12 hours. A missed dose of study medication was to be taken later up to 8 hours before the next scheduled dose; otherwise, the missed dose should not be given.

Administration of the Investigational Medicinal Product (IMP) was based on the randomized dose and subject's weight at Visit 3 (Day -1). At Visit 8 (Day 43), if the subject's weight changed  $\pm 25\%$  of the weight at Day-1, the IMP dose was recalculated. Subjects were dosed using the oral dosing syringe provided.

In order to maintain the blind across all dose groups and allow step titration to the high dose, the dose for each subject was titrated starting with a dose of ZX008 0.2 mg/kg/day (or placebo equivalent) BID. After 4 days at this dose level (Day 5), subjects randomized to the ZX008 0.8 mg/kg/day group increased their dose to 0.4 mg/kg/day while doses in the other two groups remained constant. On Day 9, the dose for the 0.8 mg/kg/day group increased to the target dose. The titration was expected to take a total of 14 days (Table 1). A new bottle of IMP was started by the subject at each level of the titration step.

Table 1: Titration Algorithm

Randomized Group	Titration Step 1 Study Day 1-4	Titration Step 2 Study Days 5-8	Titration Step 3 Study Days 9-14
ZX008 0.2 mg/kg/day	ZX008 0.2 mg/kg/day	ZX008 0.2 mg/kg/day	ZX008 0.2 mg/kg/day
ZX008 0.8 mg/kg/day	ZX008 0.2 mg/kg/day	ZX008 0.4 mg/kg/day	ZX008 0.8 mg/kg/day
Placebo	Placebo	Placebo	Placebo

Note: maximum daily dose of ZX008 is 30 mg.

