**Transition Period:**

Subjects who completed the Maintenance Period and were continuing into the open-label extension study were to be transitioned from double-blind study medication to open-label ZX008 (Table 3). Study medication was administered as equal doses BID in the morning and in the evening approximately 12 hours apart, with food. Each dose should have been separated by a minimum of 8 hours and a maximum of 12 hours. A missed dose of study medication may have been taken later up to 8 hours before the next scheduled dose; otherwise, the missed dose should not be given. Study medication was administered using the oral dosing syringe provided.

All subjects entering the open-label extension study were transitioned from their blinded daily dose (placebo, 0.2 mg/kg/day, 0.8 mg/kg/day, or 30 mg/day) to the 0.2 mg/kg dose during the 2-week interval between Visits 12 and 13, without breaking the blind. The IWR system assigned two bottles of IMP to the subject, one for each step in the transition. A new bottle of IMP was started by the subject at each level of the transition step.

Table 3. Transition Algorithm

Dose Group in Double-Blind Study	Transition Step 1 Day 1-4 after Visit 12	Transition Step 2 Days 5-14 after Visit 12
ZX008 0.2 mg/kg/day	ZX008 0.2 mg/kg/day	ZX008 0.2 mg/kg/day
ZX008 0.8 mg/kg/day	ZX008 0.4 mg/kg/day	ZX008 0.2 mg/kg/day
Placebo	ZX008 0.2 mg/kg/day	ZX008 0.2 mg/kg/day
Note: maximum daily dose of ZX008 is 30 mg.		

Subjects who had been randomized to placebo increased their dose to 0.2 mg/kg/day beginning on Day 1 of the transition (the day following Visit 12.) Subjects who had been randomized to 0.2 mg/kg/day continued to receive that dose. Subjects who had been randomized to 0.8 mg/kg/day or were receiving the maximum dose of 30 mg/day decreased to a dose of ZX008 0.4 mg/kg/day, or a maximum of 30 mg/day. After 4 days at this dose level (Day 5), these subjects decreased their dose to 0.2 mg/kg/day. Subjects were to report to the clinic on Day 15 for enrollment into the open-label extension study.

Data from the Taper or Transition period will not be included towards the planned efficacy endpoints except where specified, but will be included in the safety analyses.

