### 5.2. Safety (SAF) Population

All safety analyses will be performed on the SAF Population defined as all randomized subjects who receive at least one dose of ZX008 or placebo. Subjects will be analyzed according to the treatment group to which they were randomized.

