### 10.3. Adverse Events

An AE is defined as any unfavorable and unintended sign (including an abnormal, clinically significant laboratory finding), symptom, or disease temporally associated with the use of a medicinal (investigational) product, whether or not considered related to the medicinal (investigational) product. The period of observation for adverse events extends from the time the subject gives informed consent until the end of the titration/transition period (Visit 13). For patients who continue into the open-label extension study, AEs of special interest will continue to be monitored for up to 6 months after the last dose of study medication.

A TEAE is defined as any AE that based on start date information occurs after the first intake of study treatment. Safety tables will present TEAE data by assigned treatment group through Visit 13. All other AEs occurring after enrollment and prior to the first administration of study treatment are defined as non-treatment emergent AEs (non-TEAEs).

AEs are categorized as related or unrelated. If the AE is thought to be definitely, probably or possibly related to study drug then it is to be categorized as related. Possibly or definitely unrelated is categorized as unrelated. Any missing relationship will be considered as "related."

The severity of AEs (whether nonserious or serious AEs) will be assessed by the investigator as follows:

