**Statistical Analysis Plan**

Sponsor: Zogenix International Limited; Protocol No.: ZX008 Study 2 (ZX008-1501 and ZX008-1502)

A table will be provided for TEAEs (preferred term) where the percentage of subjects in a ZX008 arm who experience the event exceeds the percentage of subjects in the Placebo group with the event and occurs with a frequency of at least 2%.

No inferential statistical methods (i.e., methods that yield p-values) will be used to compare treatment groups on the frequency or severity of AEs.

These summaries will be provided for the T+M period.

Additionally, the following listings will be produced for all enrolled subjects:

- All AEs, events considered to be TEAE will be identified in the listing
- Serious AEs
- AEs that lead to premature discontinuation from the study
- Deaths

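### Both main SAPs replace the protocols' as-received safety grouping with randomised grouping, give no reason, and provide no as-received safety table

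*SAP*

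**What the plan says.** Section 12 of the Study 2 SAP reports the protocol rule, "Protocols 1501 and 1502 state that analyses of safety data will be presented by treatment actually received", and replaces it: "However, safety data will be presented by randomized treatment group except where noted otherwise". Section 6.9 of the Study 1 SAP makes the same change.

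The Safety population definitions carry it out. Section 5.2 of the Study 2 SAP says "Subjects will be analyzed according to the treatment group to which they were randomized", and section 5.3 of the Study 1 SAP matches. On adverse events, section 10.3 of the Study 2 SAP states "Safety tables will present TEAE data by assigned treatment group through Visit 13"; section 6.4.1 of the Study 1 SAP agrees.

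On drug supply, section 2.6 of the Study 2 SAP describes volume-blinding with three strengths (1.25, 2.5 and 5 mg/mL): "This was achieved by random assignment of different concentrations of the ZX008 oral solution", with the volume to give set by the interactive system. Section 2.7 adds "A new bottle of IMP was started by the subject at each level of the titration step".

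The cardiovascular SAPs define their analysis sets in section 4.2 of each (a modified intention-to-treat set for Study 1, a Safety Population for Study 2). Neither says whether subjects are grouped by randomised or received treatment.

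**The concern.** Analysing efficacy as randomised protects the comparison. For safety, the question is what the drug did to those who took it, so the usual choice, and the protocols' own, is treatment received. Under randomised grouping, a placebo child given an active bottle contributes any drug-related event to the placebo rate. A child randomised to ZX008 but given placebo adds an unexposed child to the ZX008 denominator. Both move the drug-placebo contrast towards no difference, which for harms favours the drug. The safety objective in both SAPs is exactly that contrast, for each dose.

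The change also stands out because it is unexplained. The same lists justify other departures, such as the revised age target and the dropped log-rank test.

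**Working it through.** **1. Is anything noted otherwise?** The override allows exceptions, so I looked for a safety output by treatment received.

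- Safety text and table lists in both main SAPs: none found.
- Actual dose: only in the Study 2 efficacy scatterplots (Figures 14.2.15.10 and 14.2.15.11, with their Japan and non-Japan versions).
- Daily intake and drug accountability: subject listings only (16.2.5.1 to 16.2.5.3 in both).
- Protocol deviations: listed by subject, with a category for non-compliance with study drug intake (Study 1 section 6.2.2, Study 2 section 5.5).

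A misdosed child might be traceable in listings, but no summary table would regroup that child.

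**2. Arm size.** Both SAPs state 40 per arm for 90% power, a difference of 40 points and an SD of 55, two-sided 0.05. Check: n = 2 × (1.960 + 1.282)² × (55/40)² = 2 × 10.51 × 1.891 = 39.7, so 40. Power at 40 is 0.902 by the normal approximation and 0.895 by the t distribution. The figure reproduces. It serves here only as a denominator.

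**3. Weight of one child.** 1/40 = 2.5 points, 2/40 = 5.0, 3/40 = 7.5.

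**4. Effect on a planned table (assumed cases).** Section 10.3 of the Study 2 SAP tabulates a term when its percentage in a ZX008 arm "exceeds the percentage of subjects in the Placebo group with the event and occurs with a frequency of at least 2" percent. Suppose one correctly dosed child in a ZX008 arm has an event, and k placebo children given that arm's drug have it too, with no true placebo events.

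| k | As randomised: ZX008 | As randomised: placebo | As received: ZX008 | As received: placebo |
|---|---|---|---|---|
| 1 | 1/40 = 2.5% | 1/40 = 2.5% | 2/41 = 4.9% | 0/39 = 0% |
| 2 | 1/40 = 2.5% | 2/40 = 5.0% | 3/42 = 7.1% | 0/38 = 0% |
| 3 | 1/40 = 2.5% | 3/40 = 7.5% | 4/43 = 9.3% | 0/37 = 0% |

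As randomised, this ZX008 arm does not exceed placebo in any row, so the term drops out unless the other ZX008 arm carries it. As received, it stays. With k false placebo events, the term is lost only if each ZX008 arm has at most k events.

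**5. What a wrong bottle delivers.** The strengths span 5/1.25 = 4-fold, equal to the ratio of the two target doses, 0.8/0.2 = 4. At an unchanged volume, the extreme mix-up could therefore turn one arm's dose into the other's. A 2-fold mix-up on 0.2 mg/kg/day gives 0.4, which is neither arm's target. A wrong bottle at titration step 1 or 2 lasts 4 of the 98 planned T+M days (4/98 = 4.1%).

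**The case against.** The strongest reply is that the rule is disclosed, internally consistent and harmless unless a dispensing error happened, and none is reported. That stands: this is a poorly chosen rule, not a hidden contradiction.

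Other parts of the reply also stand:

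- A reader might infer from the three strengths, identical appearance and successive bottles that the trial was prone to dose errors. The documents do not show this. Central assignment of bottle and volume is a control as much as a risk, and no error rate is given.
- The threshold effect is limited. It bites only for rare terms, the term would still appear in the all-TEAE table (14.3.1.2), and no p-values are attached to adverse event comparisons. The 2% ZX008-over-placebo table exists only in the Study 2 SAP.
- Intake, accountability and deviation listings already give part of what is needed.
- Moving every mixed-exposure child to the highest dose received would misclassify in turn. One 4-day bottle could carry 14 weeks of events into another arm.

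A reader might also infer that misattribution occurs without any error, since "Subjects who had been randomized to placebo increased their dose to 0.2 mg/kg/day beginning on Day 1 of the transition" and Safety tables run to Visit 13. That exposure is planned, but it is a question about the reporting window. The SAPs elsewhere confine the adverse event summaries to T+M, so those passages need reconciling in their own right. As-received grouping within T+M would not settle it.

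**Conclusion.** The point holds, conditionally, for the two main SAPs. They drop the protocols' as-received rule without a reason and leave no as-received safety table. It is not shown for the cardiovascular SAPs, which are silent on grouping.

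The size is about 2.5 points per misattributed event at 40 per arm. The 2.5% to 7.5% placebo rates above are illustrations that assume one to three misdosed children, each with an event absent from true placebo. They are not estimates, and the documents do not support a claim that the safety results are distorted. If no child received another arm's treatment, the two groupings are identical in T+M and nothing is lost.

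The dilution applies to mix-ups between placebo and active drug. A mix-up between the two ZX008 arms mainly blurs dose separation, and a 0.2 mg/kg/day child given the higher dose could even widen the 0.2-versus-placebo contrast.

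The change is worth making because the protocols already chose the better rule and returning to it is cheap.

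**What to change.** - In section 5.2 of the Study 2 SAP, group the Safety population by treatment actually received, and amend section 12 to match. At minimum, keep randomised grouping but add TEAE and AESI tables by treatment received, and state the reason for the departure.
- Make the same change in sections 5.3 and 6.9 of the Study 1 SAP for any re-reporting only. The Study 2 SAP (section 2.3) says Study 1 was reported in September 2017.
- Before unblinding, fix a rule for mixed exposure. One workable form classifies by the treatment received for most of T+M, and keeps brief single-bottle errors in the randomised group with a flag. Another prespecified rule would serve if it sets a minimum exposure.
- List every subject whose received treatment differs from the randomised one.
- State the grouping in section 4.2 of each cardiovascular SAP.
- Keep mITT as randomised.

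The cost is SAP wording and one derived variable for treatment received. Arm sizes may differ by one or two between the Safety and mITT tables, which a footnote can explain.
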